8.2 Clinical laboratory evaluation

Statistical analysis

Hematology, biochemistry parameters and their change from screening will be summarised by cohort at each available visit by means of descriptive statistics.

Shift tables presenting the number and the percentage of patients in each bivariate category (screening visit versus Visit 9) with regards to Investigator’s interpretation (Normal, NCS, CS) will be presented by cohort for all laboratory parameters.

Urinalysis parameters will be listed only.

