| Laboratory assessments | X | | | | | | | | | X | |
| Patient-reported outcomes ^g | | X | | | | | | | | X | |
| Concomitant medication | X | X | X | | X | X | X | X | X | X | |
| Serious medical events | X | X | X | X | X | X | X | X | X | X | X |
| Adverse events | X | X | X | X | X | X | X | X | X | X | X |

ETDRS: Early Treatment of Diabetic Retinopathy Study; PK: Pharmacokinetic

a. Standardized questions including (but not limited to): pain, blurred vision, change in visual acuity, redness of the eye

b. Examination will be performed after administration of study drug

c. Conjunctiva, cornea, anterior chamber including grading of cells and haze (Standardization of Uveitis Nomenclature Working Group), lens (Lens opacities classification system II) and vitreal haze (Standardization of Uveitis Nomenclature Working Group)

d. Including slit lamp biomicroscopy of the fundus

e. Day 0 blood sample will be taken 4 h ± 1 h after injection

f. Blood pressure and heart rate

g. National Eye Institute Visual Functioning Questionnaire 25 (VFQ-25), SF36™ Health Survey Version 2 (SF-36v2) and EuroQol-5 Dimensions Health Questionnaire (EQ-5D)

h: for visit 28 option to perform examinations to 2 consecutive days;

i: in case screening visit and baseline visit are on the same day (-7 up to dosing), examinations scheduled for both visits need only to be performed once and may be used for both study visits

LIST OF ABBREVIATIONS AND DEFINITIONS OF TERMS

| Abbreviation | Definition |
|---------------------|--|
| AE | Adverse event |
| AUC | Area under the plasma concentration time curve |
| BP | Blood pressure |
| CS | Clinically significant |
| C _{max} | Maximum plasma concentration |
| DHODH | Dihydroorotate dehydrogenase |
| EAU | Experimental autoimmune uveitis |
| ECG | Electrocardiogram |
| eCRF | Electronic case report form |
| ETDRS | Early Treatment of Diabetic Retinopathy Study |
| EU | European Union |
| GCP | Good clinical practice |
| GLP | Good laboratory practice |
| h | Hours |
| hERG | Human ether-à-go-go-related gene |
| HR | Heart rate |
| IC ₅₀ | Half-maximal inhibitory concentration |
| ICH | International Conference on Harmonization |
| IEC | Independent ethics committee |
| ITT | Intent-to-treat |
| IFN- γ | Interferon gamma |
| IL-17 | Interleukin 17 |
| IOP | Intraocular pressure |
| K ₃ EDTA | Tri-potassium ethylenediaminetetraacetic acid |
| MedDRA | Medical Dictionary for Regulatory Activities |
| NCS | Not clinically significant |

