6.6 Clinical Laboratory Tests

Safety laboratory tests will be performed at the time points specified in Table 1 and sent to a local laboratory. Additional tests may be performed at the discretion of the Investigator if deemed clinically appropriate. If required, samples may be sent to a central laboratory for confirmation of local results.

A full list of the clinical laboratory tests that will be performed and analyzed is presented in Section 21.1.

Any safety laboratory results outside the normal range will be repeated at the discretion of the Investigator and will be evaluated by the Investigator or designee as "clinically significant (CS)" or "not clinically significant (NCS)." Any CS value should be repeated as necessary and followed until resolution.

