Each AE or SAE reported will be assessed for severity and the date and time of onset (if available), time relationship to dosing, duration and outcome of each event will be noted.

Laboratory abnormalities are not considered AEs unless they are associated with clinical signs and symptoms or require medical intervention. Clinically significant abnormal clinical laboratory findings or other abnormal assessments that are associated with the disease being studied, unless judged by the Investigator as more severe than expected for the patient's condition, or that are present or detected at the start of the study and do not worsen, will not be reported as AEs or SAEs.

The Investigator will exercise medical and scientific judgment in deciding whether an abnormal clinical laboratory finding or other abnormal assessment is clinically significant.

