4.1 General

Descriptive statistics will be provided for all variables in the summary tables by cohorts (PP-001 0.3 µg, 0.6 µg and 1.2 µg) according to the type of variable summarized.

Quantitative variables will be summarised by using n, arithmetic mean, SD, median and range (minimum and maximum).

Categorical variables will be summarised by using frequency distributions and percentages.

| Forms | | | |
|--------------|--|------------------------------------|----------------|
| Title | | Statistical Analysis Plan Template | |
| Code | | Version | Effective Date |
| FRM_ST03_032 | | 01 | 23 Apr 2015 |
| | | 12 of 31 | |

Analysis will be performed on the treated eye only assuming that a patient is treated on one eye only.

The baseline used in the analysis for each variable is reported in the table below:

| Endpoint | Baseline |
|------------------------------------|----------------------------------|
| Electroretinography | Baseline (Day -7 up to dosing) |
| Fluorescein angiogram | Screening (Day -14 up to dosing) |
| Optical coherence tomography | Baseline (Day -7 up to dosing) |
| ETDRS | Baseline (Day -7 up to dosing) |
| Visual field | Baseline (Day -7 up to dosing) |
| Visually evoked cortical potential | Screening (Day -14 up to dosing) |
| Intraocular pressure | Baseline (Day -7 up to dosing) |
| Slit lamp examination | Baseline (Day -7 up to dosing) |
| Dilated fundoscopy | Baseline (Day -7 up to dosing) |
| Corneal endothelial microscopy | Baseline (Day -7 up to dosing) |
| Fundus photography | Baseline (Day -7 up to dosing) |
| Amsler grid | Baseline (Day -7 up to dosing) |
| Patient-reported outcomes | Baseline (Day -7 up to dosing) |
| Vital signs | Baseline (Day -7 up to dosing) |
| Laboratory assessments | Screening (Day -14 up to dosing) |

All endpoints data collected in the eCRF will be presented in the listings. PK endpoints will be listed as well.

No multiplicity adjustment will be implemented.

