The EuroQol EQ-5D-5L consists of five dimensions (mobility, self-care, usual activities, pain/discomfort, and anxiety/depression) each of which is recorded on a 5 point scale (1 to 5). The first response choice (“no problems”) is coded as a 1; the second (“slight problems”) is coded as a 2; the third (“moderate problems”) is coded as a 3; the forth (“severe problems”) is coded as a 4; the fifth (“extreme problems”) is coded as a 5 as indicated on the questionnaire. Values recorded in the eCRF will not be recoded.

Each combination of dimensions scores for a single subject is concatenated together to form the Health State (e.g. a string variable ‘11233’ for the scores in mobility=1, self-care=1, usual activities=2, pain/discomfort=3, and anxiety/depression=3).

The five dimensions will also be converted into a Health State Index on a scale of approximately 0 to 1, where scores close to 0 represent a health state of death and a score of 1 represents full quality of life. The conversion between the ordinal scores to an index will be carried out using UK weighting and using SAS programs supplied by EUROQOL.

A higher score indicates a more preferred health status. For the precision of TLFs the actual derived value will be used in all summary statistic calculations but will be listed to two decimal places. Summary statistics will be rounded based on the same decimal precisions.

The final EQ-5D question (the ‘Scored Health Today’) asks respondents to rate their present health status on a vertical 0 to 100 visual analogue scale of 20 cm, with 0 labelled as “Worst imaginable health state” and 100 labelled as “Best imaginable health state.” The scale is marked in increments of “10,” with values labelled at each decile.

| Forms | | | |
|--------------|--|------------------------------------|----------------|
| Title | | Statistical Analysis Plan Template | |
| Code | | Version | Effective Date |
| FRM_ST03_032 | | 01 | 23 Apr 2015 |
| | | | 26 of 31 |

Statistical analysis

The EuroQol-5 Questionnaire (EQ-5D-5L) Health State Index as the Scored Health, NEI-VFQ overall composite score and SF-36v2 scores as measured at baseline and Visit 9 (Day 28), will be summarised using descriptive statistics, and the change in score from the baseline visit will be calculated for each patient.

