| TABLE 14.3.2.3 | HAEMATOLOGY RESULTS: SHIFTS FROM SCREENING TO VISIT9 / SAFETY SET |
| TABLE 14.3.2.4 | BIOCHEMISTRY RESULTS: SHIFTS FROM SCREENING TO VISIT9 / SAFETY SET |
| TABLE 14.3.3.1 | VITAL SIGNS DURING THE STUDY AND CHANGE FROM BASELINE / SAFETY SET |

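### The laboratory shift tables compare only Screening with Day 28, so a transient clinically significant rating on an unscheduled post-injection sample is counted in no planned table (minor)

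*SAP*

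**What the plan says.** SAP 8.2 describes the laboratory shift analysis as "Shift tables presenting the number and the percentage of patients in each bivariate category (screening visit versus Visit 9"), by cohort, on the investigator's interpretation (Normal, NCS, CS). The titles of Tables 14.3.2.3 and 14.3.2.4 fix the same two time points, for example "HAEMATOLOGY RESULTS: SHIFTS FROM SCREENING TO VISIT9 / SAFETY SET". SAP 7.3 identifies the visit: "as measured at baseline and Visit 9 (Day 28"). SAP 4.1 sets the laboratory baseline: "Laboratory assessments | Screening (Day -14 up to dosing").

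Protocol Table 1 schedules laboratory tests twice, at Screening and Day 28: "Laboratory assessments | X | | | | | | | | | X". The SAP 3.2 schedule agrees.

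Protocol 6.6 also provides for tests outside that schedule: "Additional tests may be performed at the discretion of the Investigator if deemed clinically appropriate". On abnormal results it adds: "Any CS value should be repeated as necessary and followed until resolution". Protocol 7 limits which laboratory findings become AEs: "Laboratory abnormalities are not considered AEs unless they are associated with clinical signs and symptoms or require medical intervention".

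The SAP has no rule for unscheduled laboratory results and plans no worst post-injection category.

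**The concern.** SAP 3.6 names laboratory parameters as a safety endpoint, and safety is the primary objective of this first-in-human trial. The shift tables are the only planned tables that count patients by the investigator's laboratory rating. Protocol Appendix 2 lists laboratory values of potential concern, but no table in SAP 9.3 uses those limits.

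A table built on two fixed visits cannot show what happened between them. An extra test ordered after the injection is likely to have been ordered for a reason. If it is rated CS and has settled by Day 28, the table shows no change. The omission works in one direction only. The worst rating over a set of samples that includes Day 28 can never be better than the Day 28 rating, so leaving the other samples out can make a cohort look cleaner but never worse.

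**Working it through.** The plan states no figure on this point, so the check follows one hypothetical patient through each planned output.

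Assumptions: the patient is rated Normal at Screening. This is the expected state, because inclusion criterion 2 requires laboratory values in the normal range. An unscheduled sample after injection is rated CS, without signs or symptoms and without need for intervention. The patient is rated Normal again at Day 28.

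1. **Shift tables 14.3.2.3 and 14.3.2.4 (SAP 8.2).** Only the Screening and Visit 9 ratings enter. The patient is counted as Normal to Normal. If the Day 28 rating were NCS, the cell would be Normal to NCS; in either case the CS rating is not counted.
2. **By-visit summaries, Tables 14.3.2.1 and 14.3.2.2 (SAP 8.2).** These give descriptive statistics for values and changes at visits with data. The SAP does not say whether an unscheduled sample is a visit. The value might appear here, but the CS rating would not be counted.
3. **AE tables (Protocol 7).** With no signs or symptoms and no intervention, the finding is not an AE and does not reach Tables 14.3.1.1 to 14.3.1.6.
4. **Listings 16.2.8.1 and 16.2.8.2 (SAP 4.1 and 9.5).** SAP 4.1 has the endpoint data in the eCRF listed, so the result appears here if it was entered.

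Size, for a cohort of four with one such patient and the other three rated Normal throughout:

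| Cell | Planned table (Screening vs Day 28) | Screening vs worst post-injection |
|---|---|---|
| Normal to Normal | 4/4 = 100% | 3/4 = 75% |
| Normal to CS | 0/4 = 0% | 1/4 = 25% |

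If no unscheduled sample is taken, the only post-injection rating is the one at Day 28 and the two columns are identical. Scheduled laboratory time points number 2, and both are in the table, so 0 scheduled time points are left out. The documents give no frequency for unscheduled sampling, so the chance that the columns differ cannot be calculated.

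A related case is a patient who leaves before Visit 9 but has an unscheduled post-injection rating. SAP 4.7 places that patient in the Missing category. The patient is visible as missing, but the rating that exists is not used.

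**The case against.** A reader might infer from a Screening-to-Day-28 table that planned interim laboratory data are being discarded. They are not, because none are planned. The gap opens only if several conditions hold together: an unscheduled sample, a CS rating, no associated signs or symptoms, no intervention, and a better rating at Day 28. A test prompted by a complaint may well meet the AE condition in Protocol 7, whose general AE definition also covers abnormal laboratory findings. The protocol further expects systemic exposure close to or below the assay's limit of detection (section 3.2), so drug-related laboratory changes are not anticipated.

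Nor is the result hidden. With cohorts of four in a descriptive, open-label study, a reader of the listings can inspect every patient. The table shells are in a separate appendix that is not among the documents and may deal with unscheduled samples. Finally, a worst-value shift is a convention with its own weakness: patients sampled more often have more chances to show an abnormality.

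Most of this stands, and it sets the weight of the point. It does not remove it. The SAP text and the table titles are explicit about the two visits, and listing a finding is not the same as counting it. The uneven-sampling weakness is met by showing both panels side by side rather than replacing one with the other.

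**Conclusion.** The point holds as a minor reporting gap. A CS rating on an unscheduled post-injection sample that is no longer CS at Day 28, and that does not qualify as an AE, is counted in no planned table. In a cohort of four, one such patient is the difference between 0% and 25% in the Normal to CS cell. This rests on three assumptions: that such a sample is taken, that it is rated CS, and that the unseen shells contain no rule for it.

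Three stronger readings should be set aside:

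- **Repeat samples as a second route.** Protocol 6.6 ties repeats to results already out of range. Before Day 28, a repeat can follow only an abnormal Screening result or an unscheduled sample, and a repeat of the Day 28 sample is not earlier than Day 28. Repeats add no separate case.
- **Early leavers dropping out of the tables.** SAP 4.7 has them shown as Missing.
- **Day 28 being too late to detect an effect.** Day 28 is 28 × 24 = 672 h after injection. At the rabbit plasma half-lives of 5 to 6 h in Protocol 1.3.2, that is 672/6 = 112 to 672/5 = 134 half-lives, if human values are similar. This concerns the sampling schedule. It does not show that the shift table mishandles the data collected, and the change proposed here would not alter it.

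**What to change.** In SAP 8.2 and Tables 14.3.2.3 and 14.3.2.4, keep the Screening versus Day 28 shift as the first panel. Add a second panel of Screening versus the worst post-injection investigator rating (Normal < NCS < CS) over all scheduled and unscheduled samples. A patient without a Day 28 sample but with any post-injection rating then contributes to the second panel. Flag unscheduled results in Listings 16.2.8.1 and 16.2.8.2.

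The approach is not foreign to the plan: Protocol 9.6 asks for the worst value after baseline for vital signs, although SAP 8.3 does not carry this over.

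The cost is a few lines of SAP text, two table shells and a listing flag, with no new data collection. The downside is the uneven-sampling effect described above. A footnote giving the number of patients with any unscheduled sample in each cohort would let the reader judge it.

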8.3 Vital signs

Statistical analysis

Systolic Blood Pressure (mmHg), Diastolic Blood Pressure (mmHg), Heart Rate (beats/min) and their change from baseline will be summarised by cohort at each available visit by means of descriptive statistics.

8.4 ECGs

Statistical analysis

Heart rate (beats/min), PR interval (msec), QRS Duration (msec), QTc interval (msec), QTcf (msec) and the Investigator’s interpretation (Normal, NCS, CS) will be listed only.

8.5 Physical examination

Statistical analysis

Physical examination will be listed only.

| Forms | | | |
|--------------|---------|------------------------------------|----------|
| Title | | Statistical Analysis Plan Template | |
| Code | Version | Effective Date | Page |
| FRM_ST03_032 | 01 | 23 Apr 2015 | 28 of 31 |

8.6 Other safety evaluations

Not foreseen.

9. Tables, Figures and Listings

9.1 Programs and tables quality control

The statistician-programmer of the tables, listings and figures will carefully review the programs and will verify that no error message is highlighted in the 'LOG' file.

Moreover, a second statistician-programmer will verify the internal consistency of each table by checking the results using different SAS programs.

The following level of validation will be implemented:

- Validation of statistical datasets: via validation of the final output (tables)
- Validation of statistical output:
 - tables: independent programming, with a comparison of the results against the initial output;
 - listings: peer review.

9.2 Programming conventions

All tables/figures/listings will be presented in landscape format.

The standard font size is 9 points Arial for all tables. Listings will be presented with an 8 or 7 points Arial.

Titles will be center-aligned; footnotes will be left-aligned.

Each table/figure/listing will have 2 titles:

- The 1st title will be the table/figure/listing number with the description of the table/figure/listing;
- The 2nd title will be a description of the study set presented in the table/figure/listing.

Some tables will have a third title (before 2nd title) with a description of the statistical method used in those tables.

Any footnote added to explain the table/listing/figure contents will be presented in the following format:

Note 1: Percentages are calculated on the number of patients (N).

Note 2: A serious adverse event is an

Note 3:

The last two footnotes of each table/figure will be footers indicating:

- the reference listing of the data;
- the program name, the date and time of generation and the SAS® version used.

The last footnote of each listing will be a footer indicating the program name, the date and time of generation and the SAS® version used.

| Forms | | | |
|--------------|---------|------------------------------------|----------|
| Title | | Statistical Analysis Plan Template | |
| Code | Version | Effective Date | Page |
| FRM_ST03_032 | 01 | 23 Apr 2015 | 29 of 31 |

Unless otherwise stated, listings will be presented by the only treatment and sorted by the patient number.

All the listings will be based on the Safety set, except stated otherwise.

The derived variables will be identified in the listings with a flag (*).

In general, dates will be presented on listings in the format ddmmmyyyy (date9.) and time in the format hh:mm (time5.). In case of partial dates or times, missing information will be replaced by dashes. Numeric variables will be listed generally with the same number of decimal places as in the actual data.

The following rules on decimal places will be considered in the listings for the derived variables (in the analyses approximations will not be performed):

- Age (years): 0 decimal place;
- BMI (kg/m²): 1 decimal place;
- change from baseline: same as the variable considered.

The following rules on decimal places will be considered for the results of the analyses (if the analyses are performed on derived variables, the level of precision of the actual data is derived from the previous list):

- Min, max: same as actual data;
- Mean and its confidence limits (unadjusted and adjusted), SD, median: actual data + 1 decimal;
- Percentage: 1 decimal place;
- P-value: 3 decimal places.

9.3 Tables

The list of tables is provided here below:

| TABLE | TITLE |
|----------------|---|
| TABLE 14.1.1 | SUBJECT DISPOSITION / SUMMARY OF ALL SUBJECTS |
| TABLE 14.1.2.1 | PRIMARY REASONS FOR DISCONTINUATION FROM STUDY / SAFETY SET |
| TABLE 14.1.3.1 | ANALYSIS SETS / SAFETY SET |
| TABLE 14.1.4.1 | DEMOGRAPHIC CHARACTERISTICS / SAFETY SET |
| TABLE 14.1.5.1 | MEDICAL AND OPHTHALMIC HISTORY: PAST DISEASES / SAFETY SET |
| TABLE 14.1.5.2 | MEDICAL AND OPHTHALMIC HISTORY: CONCOMITANT DISEASES // SAFETY SET |
| TABLE 14.1.6.1 | PREVIOUS MEDICATIONS / SAFETY SET |
| TABLE 14.1.6.2 | CONCOMITANT MEDICATIONS / SAFETY SET |
| TABLE 14.2.2.1 | ETDRS SCORES DURING THE STUDY AND CHANGE FROM BASELINE / SAFETY SET |
| TABLE 14.2.2.2 | ETDRS SCORES DURING THE STUDY AND CHANGE FROM BASELINE / PP SET |

| Forms | | | | |
|--------------|--|------------------------------------|----------------|----------|
| Title | | Statistical Analysis Plan Template | | |
| Code | | Version | Effective Date | Page |
| FRM_ST03_032 | | 01 | 23 Apr 2015 | 30 of 31 |

| TABLE | TITLE |
|----------------|---|
| TABLE 14.2.3.1 | SLIT LAMP EXAMINATION DURING STUDY / SAFETY SET |
| TABLE 14.2.4.1 | FLUORESCEIN ANGIOGRAM, ETDRS, VISUALLY EVOKED CORTICAL POTENTIAL, INTRAOCCULAR PRESSURE AND DILATED FUNDOSCOPY DURING STUDY / SAFETY SET |
| TABLE 14.2.5.1 | ELECTRORETINOGRAPHY, OPTICAL COHERENCE TOMOGRAPHY, VISUAL FIELD, CORNEAL ENDOTHELIAL MICROSCOPY, FUNDUS PHOTOGRAPHY AND AMSLER GRID DURING STUDY / SAFETY SET |
| TABLE 14.2.6 | PATIENT- REPORTED OUTCOMES DURING THE STUDY AND CHANGE FROM BASELINE / SAFETY SET |
| TABLE 14.3.1.1 | SUMMARY OF TREATMENT EMERGENT ADVERSE EVENTS / SAFETY SET |
| TABLE 14.3.1.2 | TREATMENT EMERGENT ADVERSE EVENTS BY SYSTEM ORGAN CLASS AND PREFERRED TERM / SAFETY SET |
| TABLE 14.3.1.3 | TREATMENT EMERGENT SERIOUS ADVERSE EVENTS BY SYSTEM ORGAN CLASS AND PREFERRED TERM / SAFETY SET |
| TABLE 14.3.1.4 | TREATMENT EMERGENT ADVERSE DRUG REACTIONS BY SYSTEM ORGAN CLASS AND PREFERRED TERM / SAFETY SET |
| TABLE 14.3.1.5 | TREATMENT EMERGENT ADVERSE EVENTS LEADING TO DISCONTINUATION BY SYSTEM ORGAN CLASS AND PREFERRED TERM / SAFETY SET |
| TABLE 14.3.1.6 | TREATMENT EMERGENT ADVERSE EVENTS LEADING TO DEATH BY SYSTEM ORGAN CLASS AND PREFERRED TERM / SAFETY SET |
| TABLE 14.3.2.1 | HAEMATOLOGY RESULTS DURING THE STUDY AND CHANGE FROM SCREENING / SAFETY SET |
| TABLE 14.3.2.2 | BIOCHEMISTRY RESULTS DURING THE STUDY AND CHANGE FROM SCREENING / SAFETY SET |
| TABLE 14.3.2.3 | HAEMATOLOGY RESULTS: SHIFTS FROM SCREENING TO VISIT9 / SAFETY SET |
| TABLE 14.3.2.4 | BIOCHEMISTRY RESULTS: SHIFTS FROM SCREENING TO VISIT9 / SAFETY SET |
| TABLE 14.3.3.1 | VITAL SIGNS DURING THE STUDY AND CHANGE FROM BASELINE / SAFETY SET |

